Consenting patients will be randomized to a study arm (Exparel single injection TAP block or TAP block catheter). Randomization will be performed based on a random number generator (1 or 2) and after patient is consented. Group 1 will be deemed the Exparel single shot group while Group 2 is the TAP catheter group. Both procedures are performed by the acute pain service with an anesthesiology faculty member and an anesthesiology resident on the rotation that month under direct supervision. When patients are enrolled into the study, the TAP block for both arms will be performed in the preoperative holding area, prior to induction of general anesthesia. Prior to any procedure, a preoperative evaluation is performed, consent is verified, procedural time out is performed, and emergency medications are available if there are signs of local anesthetic toxicity. For each patient, maximum allowable doses of local anesthetic will be calculated as to avoid the risk of any possible local anesthetic overdose.

The Exparel TAP block dose will be provided by inpatient pharmacy and will consist of 266 mg of Exparel (1.3% in 20cc) diluted to 60 ml total volume with 40 ml of preservative free normal saline. An injection of 30 ml of volume will be performed on each side, with a total of 60ml for bilateral TAP blocks. Exparel is currently FDA approved for surgical site infiltration and the classification of TAP blocks as surgical field blocks was specified in a FDA letter in fall 2015. This is the current standard dilution and volume used in other academic centers for Exparel TAP blocks.

For those randomized to the TAP catheter group, 30 ml of 0.5% ropivacaine will be diluted with an additional 30 ml of preservative free normal saline for a total volume of 60cc, with 30 ml injected into each side. We will also place peripheral nerve catheters, approximately 3-5cm into the TAP space after injection of the ropivacaine solution. Catheters will be secured to the skin with tegaderm tape. Infusions will be ordered with CADD pumps and will be initiated at a rate of 8 ml/hr of 0.2% ropivacaine on the inpatient floor.

Postoperatively, patients will be monitored in the PACU per routine care. Patients will be ordered a combination of standardized short acting opioids (fentanyl), and long acting opioids (hydromorphone) in addition to anti-emetics (ondansetron 4mg IV) for administration if needed in the PACU. In the PACU, perioperative nursing staff will dose medications accordingly to the EMR orders and the PACU clearance time will be logged as well. PACU duration is calculated as the time interval between patient arrival into the PACU and when the patient is signed out of the PACU by the PACU anesthesiology resident/faculty.

PROTOCOL TITLE: Transversus abdominus plane (TAP) block catheters vs liposomal bupivacaine for pain control after colorectal surgery: A prospective randomized control trial

Post-PACU hospital course will proceed as is standard of care with PRN pain medication. Patient with single shot Exparel TAP blocks will be seen on the inpatient floor for two days after the surgery to assess for postoperative pain control. Patients with TAP catheters will also be seen daily until the catheters are removed by the acute pain service and when the patient is tolerating an oral diet and there are no overt signs of postoperative ileus. Standard hospital discharge criteria will be used for both groups.

Information will be collected from the patients' hospital stays, including Ultrasound imaging of the patient's TAP block, intraoperative anesthesia record, the amount of opioid use in morphine oral equivalents in the first 6, 12, 18, and 24, 36, and 48 hours after surgery, incidence of nausea/vomiting, pain score averages from EMR Epic RN Pain data, PACU clearance time and length of hospital stay.

8) Data and/or Specimen Management and Confidentiality

During the study phase, patient information will be stored electronically via a password protected database on the UC Davis OneDrive cloud storage folder. Only authorized study staff will have access to the file while access to the UC Davis OneDrive folder requires UC Davis login. Patients' information will be stored on a secure database with indirect identifiers, such as patient 1, patient 2, etc. There will be a separate password protected document that contains the indirect and direct identifiers to match the two. After the study has been closed, consents will be maintained for three years, and HIPAA consents for six years, in compliance with IRB rules and regulations. Any data obtained from the Electronic Medical Record (EMR) will be identified by subject ID only and collected onto an encrypted spreadsheet on the PI's password protected computer.

Statistical analysis plan & Sample size calculation

The primary outcome measure will be the between group difference in opioid consumption in the first 48 hours surgery.

We anticipate superior pain control in the Exparel group based on the potential for TAP catheter problems such as catheter dislodgement and lack of timely infusion refill. A difference in 20% of opioid oral morphine equivalents will be considered clinically significant. Prior reports (Carney et al) suggest a difference of $55.3\text{mg} \pm 17.6$ in the control group versus $26.8\text{mg} \pm 19.8$ in the TAP block group. Using a power of 0.8 and $p < 0.05$ as statistically significant yields a sample size of 44 per group to show significance. We will enroll 100 to allow for early withdrawal or protocol violations, with planned interim analysis at $n=20$ of each group completing the study (40 patients) to allow sample size refinement as needed. Data will be analyzed for normal distribution. Normally distributed data will be compared using a T-test for the 2 groups; data that is not normally distributed will be compared using the Mann Whitney U test. Categorical data will be compared by Chi square.

PROTOCOL TITLE: Transversus abdominus plane (TAP) block catheters vs liposomal bupivacaine for pain control after colorectal surgery: A prospective randomized control trial

All data will be stored online in the secure UC Davis OneDrive folder with password protected files. All research staff will have completed HIPAA – related training and IRB – related training.

9) Provisions to Monitor the Data to Ensure the Safety of Subjects

Patients will be monitored closely in the PACU prior to discharge to the inpatient floor for any signs and symptoms of local anesthetic toxicity, abdominal pain, or allergic reaction. The dose of local anesthetic given will be calculated to be less than the toxic dose level for ropivacaine (2-3mg/kg) and liposomal bupivacaine (2-3mg/kg). Patients receiving TAP catheters will be seen daily by the acute pain service who will visually inspect the site of insertion and assess the patient for any abdominal pain.

Any adverse events, such as intravascular injection, allergic reaction, or other unanticipated event will be assessed for its causative relationship to the TAP block by the PI ([name]).

If a serious adverse event occurs, it will be reported immediately to the IRB and will trigger an immediate suspension in enrollment and a review of the injection protocol with the Chiefs of both the Departments of Anesthesiology and Colorectal Surgery. If any performer error can be identified and corrected, then with approval from the departments enrollment will continue. If not, the study will be terminated.

Any unexpected adverse events will be documented and reported to the IRB as well as study participants.

We will cumulatively review the data after 20 subjects in each study arm have been enrolled, and then again at 50 patients, 75 patients, 100 patients until study completion. Data will be reviewed for any adverse effects from TAP blocks, pain scores, opioid consumptions, other additional secondary outcome measures such as nausea/vomiting.

PROTOCOL TITLE: Transversus abdominus plane (TAP) block catheters vs liposomal bupivacaine for pain control after colorectal surgery: A prospective randomized control trial

10) Withdrawal of Subjects

Because this is a study comparing a single injection versus a peripheral nerve catheter, patients receiving a single injection are able to withdraw voluntarily any time prior to the injection. If there was difficulty with visualization of the TAP plane with ultrasound due to body habitus, then the patient will be withdrawn from the study. At all instances, patient safety will be the primary priority above all over study parameters.

With the TAP catheter group, patients may withdraw voluntarily from the study if they wish.

11) Risks to Subjects

A possible risk is the TAP block not providing adequate pain control postoperatively. Patients will have access to routine IV and oral pain medications including opioids, acetaminophen, NSAIDS, and other multimodal adjuncts. Complications after TAP blocks are rare, and there are no known reports of local anesthetic toxicity after TAP block injections. There have been case reports of liver laceration with inadvertent injury by the injection needle while performing TAP blocks. There is also one case report of catheter placement into the peritoneal cavity, although there was no injury to any organs. The likelihood of any needle placement errors is minimized by ultrasound visualization of the TAP plane and the needle. Any adverse event is less likely with careful aseptic technique, performance of a procedural time-out prior to the block, and careful aspiration prior to injection of any local anesthetic.

The use of Exparel has been shown to have no greater incidence of adverse events compared to plain bupivacaine based on 10 randomized control trials with 823 subjects comparing the two.

Allergic reactions/toxicity from local anesthetics are extremely rare, and symptoms can range from itching, swelling, difficulty breathing, abnormal heartbeat, and in extreme cases, death.

TAP catheters have an inherent risk of hematoma formation, dislodgement and infection due to the nature of having a foreign body catheter in the TAP plane of a patient.

12) Potential Benefits to Subjects

Patients may have decreased postoperative pain control with either of the TAP blocks. They may also have decreased intraoperative opioid use as well as less postoperative opioid utilization, which in addition to better pain control may lead to less opioid – related side effects including pruritus, decreased incidence of opioid related constipation and ileus, nausea and vomiting.

PROTOCOL TITLE: Transversus abdominus plane (TAP) block catheters vs liposomal bupivacaine for pain control after colorectal surgery: A prospective randomized control trial

13) Sharing of Results with Subjects

No additional information will be shared with research subjects

14) Provisions to Protect the Privacy Interests of Subjects

Patients will be approached about enrolling in this study in the preoperative area. The person obtaining consent will be a research team member from Anesthesiology and/or Surgery departments. Patient beds in this area are one bed per room; therefore, the conversation will be in private, between the research staff and patient. Family members may be present, but this is standard for all preoperative consents (anesthesia consents, block consents, sometimes surgical consents if they are not on file). The consent process will specifically state that refusal to enroll will not result in any penalty, including any withholding of pain medication in the future. Post-operatively, patient privacy will be protected and only study personal will have access to the encrypted study database with patient data.

15) Compensation for Research-Related Injury

There is no specific compensation for study participation. TAP blocks are a billable procedure and used routinely for postoperative pain control in colorectal surgery patients. Any possible complications related to the procedure will be covered by insurance.

16) Economic Burden to Subjects

No economic burden to patients as TAP blocks are already planned for these patients' surgical operations. Exparel is FDA approved for this use. UCDMC formulary restricts Exparel use and requires IRB approval for this application. Within an IRB approved protocol the medication would be billed for as with all other medications given to the patient. There is no additional leave time planned for patients and these procedures will decrease the patients' postoperative pain control and may allow them to be discharged sooner.

17) Drugs or Devices

The study medication, liposomal bupivacaine (Exparel) will be obtained from the inpatient pharmacy prior to administration of the TAP block. All anesthesiologists performing the TAP block will have had prior education about the proper administration and dilution of the Exparel single shot injections. If the patient is receiving TAP block catheters, then the ropivacaine 0.25% medication is obtained from the acute pain block cart per protocol by the pain service.

18) [ClinicalTrials.gov](https://clinicaltrials.gov) Registration

Section 1: NIH Funded Studies

PROTOCOL TITLE: Transversus abdominus plane (TAP) block catheters vs liposomal bupivacaine for pain control after colorectal surgery: A prospective randomized control trial

If yes to BOTH, the study must be registered on Clinicaltrials.gov.

Yes	
	This study is funded by the NIH . (If this study is not funded by NIH, go to Section 2.)
	One or more human subjects will be prospectively assigned to one or more interventions (which may include placebo or other control) to evaluate the effects of those interventions on health-related biomedical or behavioral outcomes.

Section 2: Studies subject to FDA jurisdiction

If yes to ANY the study must be registered on Clinicaltrials.gov.

Yes	
	This is a prospective clinical study of health outcomes in human subjects that compares an intervention with an FDA-regulated device against a control. This is not a small clinical trial to determine the feasibility of a device, or a clinical trial to test prototype devices where the primary outcome measure relates to feasibility and not to health outcomes.
	This is a pediatric postmarket surveillance of a device as required under section 522 of the Federal Food, Drug, and Cosmetic Act.
	This is a controlled clinical investigation, other than a phase I clinical investigation, of a drug subject to section 505 of the Federal Food, Drug, and Cosmetic Act or to section 351 of the Public Health Service Act.

To view a flowchart describing applicable clinical trials subject to FDA jurisdiction click [here](#).

Section 3: Publishing the results

If yes to BOTH the study must be registered on Clinicaltrials.gov.

Yes	
	This study prospectively assigns people or a group of people to an intervention, with or without concurrent comparison or control groups, to study the cause-and-effect relationship between a health-related intervention and a health outcome.
	The PI has access to and control over all the data from the clinical trial and has the right to publish the results of the trial and plans to publish the results in a journal that follows the ICMJE recommendations .

This requirement includes studies of behavioral interventions.

Section 4: Registration on Clinicaltrials.gov is not required

Yes	
	I have read sections 1-3 above and registration on clinicaltrials.gov is not required for this research.

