PROTOCOL TITLE: Transversus abdominus plane (TAP) block catheters vs liposomal bupivacaine for pain control after colorectal surgery: A prospective randomized control trial

1) Protocol Title

Transversus abdominus plane (TAP) block catheters vs liposomal bupivacaine for pain control after colorectal surgery: A prospective randomized control trial

Protocol Version Date: 1/31/17

2) Objectives

- i) Primary: Compare the use of TAP blocks with ropivacaine bolus and ropivacaine catheters versus single shot TAP blocks with liposomal bupivacaine
 - (1) We anticipate superior efficacy and pain control with liposomal bupivacaine TAP blocks measured by use of opioids (measured in oral morphine equivalents) in the first 48 hours following surgery.
- ii) Secondary:
 - (1) Assess the efficacy and safety of TAP blocks for pain control after colorectal surgery in a prospective fashion
 - (a) Hypothesis: Anticipate satisfactory pain control in both TAP block groups for somatic abdominal pain measured as proportion of pain scores in the mild range (up to 4 out of 10 pain documented in nursing notes)
 - (b) Anticipate equivalent side effects measured as duration of ileus, rash, itching, nausea/vomiting.
 - (2) Compare the pharmacological costs and medical utilization costs of TAP block catheters versus single shot injection of TAP block with liposomal bupivacaine
 - (a) Anticipate lower medical utilization costs with single shot injection with liposomal bupivacaine TAP blocks
 - (b) Measured as acquisition cost of drugs and supplies

3) Background

Pain control after abdominal laparoscopic surgery involves multiple components of somatic and visceral pain. Although opioids are commonly used for acute postoperative pain control, opioid – induced constipation that can increase the risk of postoperative ileus, nausea, and pruritus are significant side effects that may prolong hospital length of stay. Multimodal analgesic regimens have been shown to increase pain control while sparing the use of systemic opioids. These have included modalities such as acetaminophen, non-steroidal anti-inflammatory drugs, and peripheral nerve blocks.

The transversus abdominus plane block (TAP) is a minimally invasive ultrasound guided peripheral nerve block that is helpful in decreasing somatic abdominal pain after surgery

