PROTOCOL TITLE: Transversus abdominus plane (TAP) block catheters vs liposomal bupivacaine for pain control after colorectal surgery: A prospective randomized control trial

and decreases opioid consumption while improving pain control. TAP involves local anesthetic infiltration between the internal oblique and the transversus abdominis plane in which space the terminal branches of the anterior roots of the lower six thoracic and first lumbar nerves course. These nerves innervate the anterolateral abdominal wall. In colorectal surgery patients, TAP have resulted in a decrease in 24-hour morphine consumption as well as earlier discharge and return to diet time compared to patient controlled analgesia (PCA).

At UC Davis, it is standard practice to place TAP blocks with catheters for adult colorectal surgery patients for perioperative pain control. In many cases, the TAP catheters will remain in the patient for two days and are removed when the patient's somatic pain is controlled and they are able to tolerate oral intake. However, it is resource intensive requiring the use of two sterile peripheral nerve catheter kits, two CADD infusion pumps, nursing time to replace the ropivacaine infusion cassette every 8-10 hours, and 30-40 minutes of physician time for block placement with additional physician time needed for ongoing catheter management. There is also a risk of catheter – related complications including inadvertent dislodgement, catheter infections, and increased burden to the patient from the two additional catheters tethered to the patient.

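### The 44 per group fits a 20% difference only when the base is the cited control mean; if the catheter arm resembles the cited TAP-block group, two-sided power is about 24–33%, not 80%

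*Combined protocol and SAP*

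**What the plan says.** The calculation is in the part of section 8 headed Statistical analysis plan & Sample size calculation. The primary outcome is the between-group difference in opioid use over 48 hours. The target is: "A difference in 20% of opioid oral morphine equivalents will be considered clinically significant". A prior report is cited with 55.3 mg ± 17.6 in a control group and 26.8 mg ± 19.8 in a TAP-block group. The plan then says that power 0.8 and p < 0.05 "as statistically significant yields a sample size of 44 per group to show significance". It enrols 100 to cover losses and plans an interim look at 20 per group "to allow sample size refinement as needed". The test is a t-test for normal data; otherwise, "data that is not normally distributed will be compared using the Mann Whitney U test".

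The comparison itself is set in section 2 (primary objective): "Compare the use of TAP blocks with ropivacaine bolus and ropivacaine catheters versus single shot TAP blocks with liposomal bupivacaine". Section 7 says that "the TAP block for both arms will be performed in the preoperative holding area". The Background (section 3) says that in colorectal patients "TAP have resulted in a decrease in 24-hour morphine consumption", and of the site's usual practice: "In many cases, the TAP catheters will remain in the patient for two days".

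**The concern.** A relative difference becomes a number of milligrams only once a base mean is chosen. The plan lists two means and two SDs but does not say which of them entered the calculation, and it does not state sidedness. The stated 44 therefore cannot be checked as written.

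The likely base is also doubtful. The cited control group is the one contrasted with TAP block, whereas in this trial both arms get a block and the comparator adds a continuous infusion. If opioid use in the catheter arm is nearer the cited TAP-block figure, 20% of it is a much smaller difference while the SD is no smaller. A true 20% reduction would then usually be missed, and a non-significant result could be misread as showing no relevant difference.

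**Working it through.** **Inputs.** From the sample-size paragraph: alpha 0.05; power 0.80; means 55.3 and 26.8 mg; SDs 17.6 and 19.8 (the ± values are read as SDs); 44 per group; 100 enrolled. Assumptions: 1:1 allocation, so 50 per group enrolled; a common SD between 17.6 and 19.8, with root-mean-square √[(17.6² + 19.8²)/2] = 18.73.

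**Step 1: reproduce 44.** Normal approximation, two-sided:

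n per group = 2(1.96 + 0.8416)² SD² / Δ² = 15.70 × SD² / Δ²

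With Δ = 0.20 × 55.3 = 11.06 mg and SD 18.73: 15.70 × 350.9 / 122.3 = 45.0. The t-test solution is 46.0. The t-test solutions for every base the paragraph offers, at SD 17.6 / 18.73 / 19.8, are:

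| Target difference | Δ (mg) | n per group, two-sided | n per group, one-sided |
|---|---|---|---|
| 20% of control mean 55.3 | 11.06 | 40.7 / 46.0 / 51.3 | 32.0 / 36.2 / 40.3 |
| 20% of midpoint 41.05 | 8.21 | 73 / 83 / 92 | 57.5 / 65.0 / 72.6 |
| 20% of the 28.5 mg difference | 5.70 | 151 / 171 / 190 | 119 / 134 / 150 |
| 20% of TAP-block mean 26.8 | 5.36 | 170 / 193 / 215 | 134 / 152 / 169 |
| Whole 28.5 mg difference | 28.5 | 7.1 / 7.9 / 8.7 | 5.5 / 6.1 / 6.8 |

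Only the control mean comes near 44. Every other row gives 57 or more, or 9 or fewer.

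**Step 2: power if the catheter arm resembles the cited TAP-block group.** Δ = 0.20 × 26.8 = 5.36 mg, n = 44 per group.

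- SD 19.8: SE = 19.8 × √(2/44) = 4.22; 5.36/4.22 − 1.96 = −0.69; power 24.5% (t-test 24.1%).
- SD 17.6: SE = 3.75; 5.36/3.75 − 1.96 = −0.53; power 29.8% (t-test 29.2%).
- One-sided t-test over the same SDs: 35–41%.

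For skewed data, 100,000 trials per setting were simulated with mean 26.8, SD 19.8 and every value in one arm multiplied by 0.8. Gamma data gave 28% (t-test) and 25% (Mann-Whitney); lognormal data gave 30% and 33%. With the normal-data t-test at 24%, the range is 24–33%. Pairing 26.8 mg with the control group's SD of 17.6 gives 29–39% over the same tests and distributions.

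**Step 3: other catheter means.** Two-sided t-test for a 20% difference, SD 19.8 to 17.6 held fixed. The 40 and 50 mg values are illustrative.

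| Catheter mean (mg) | Power, 44 per group | Power, 50 per group |
|---|---|---|
| 26.8 | 24–29% | 27–33% |
| 40 | 47–56% | 52–61% |
| 50 | 65–75% | 71–80% |
| 55.3 | 74–83% | 79–88% |

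**Step 4: what 44 per group can detect.** The standardised difference detectable with 80% power is 0.604 two-sided, which is 10.6–12.0 mg. As 20% of a mean, that needs a catheter mean of 53.2–59.8 mg (five times the unrounded difference).

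**Step 5: if the SD scales with the mean.** Power then depends only on SD/mean. At 44 per group, two-sided: ratio 0.32, 83%; 0.40, 64%; 0.50, 46%; 0.60, 34%; 0.74, 24%. Power of 80% needs at most 0.2/0.604 = 0.33 (one-sided 0.2/0.534 = 0.37). The cited control group has 17.6/55.3 = 0.32; the cited TAP-block group has 19.8/26.8 = 0.74.

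**Step 6: precision.** The 95% CI half-width at 44 per group is 1.988 × SE = 7.5–8.4 mg, wider than 5.36 mg. In the Step 2 case, an observed difference of zero would not exclude a 20% benefit.

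**The case against.** The strongest reply is that 44 is not a slip of calculation. It is reproduced within about two patients from 20% of 55.3 mg with an averaged SD, so the dispute is about an unstated and debatable base. That base is itself inferred: no stated SD gives exactly 44, and a generic standardised difference of 0.6 also gives 44 (15.70/0.36 = 43.6). This stands as a limit on what can be said about the planners' reasoning. It does not rescue the 80%: a standardised difference of 0.6 is 20% of the mean only if SD/mean is about 0.33.

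Second, the low-power case may be too pessimistic. The plan expects catheter dislodgement and late refills, and infusions start only on the inpatient floor, so the catheter mean may exceed that of a working block. The Background's evidence on morphine use concerns 24 hours against patient-controlled analgesia, not this 48-hour outcome. That is fair, and it is why the conclusion is conditional. But even at the midpoint of the two cited means (41.05 mg), two-sided power is 49–58% (61–70% one-sided).

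Third, the cited time window and opioid units are not given, so 48-hour oral equivalents could be larger. A larger mean helps only if the SD does not grow in proportion, and a change of units leaves SD/mean unchanged.

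Fourth, the interim look could correct the size. It has no rule, target or base mean, so by itself it does not support the stated 80%.

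**Conclusion.** The concern holds. The plan states 80% power without condition, yet 44 per group is approached only from the mean of a group that the plan contrasts with TAP block. The only figures it cites for patients with a block give about 24–33% two-sided power for the difference it calls clinically significant. In that case a true 20% reduction would be missed in about 67–76% of such trials. If the test were one-sided, the t-test figure would be 35–41%, still far from 80%.

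This rests on the catheter arm resembling the cited TAP-block group in mean and SD, which the documents neither state nor rule out. The statement of power for the primary outcome needs correcting.

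**What to change.** Keep enrolment at 100 and restate the paragraph, for example:

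> The 20% difference is relative to mean 48-hour oral morphine equivalents in the TAP catheter group. With 44 evaluable patients per group (two-sided t-test, alpha 0.05), the difference detectable with 80% power is about 10.6–12.0 mg for an SD of 17.6–19.8 mg. Power for a 20% difference depends on the catheter-group mean, which is not yet known: 24–29% at 26.8 mg, 47–56% at 40 mg, 65–75% at 50 mg and 74–83% at 55.3 mg. The SDs and the 26.8 and 55.3 mg means come from a prior report and are assumptions; its time window and units are to be confirmed.

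Add that the primary difference will be reported with its 95% CI, and that a non-significant result will not be read as excluding a 20% difference.

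At the 40-patient look, update the stated power or detectable difference with the pooled SD and a base mean that matches the definition. That is the catheter-group mean or, if the look is blinded, the pooled mean divided by 0.9, because under a 20% reduction the pooled mean is (1 + 0.8)/2 = 0.9 of the catheter mean. Any change in enrolment is a separate decision.

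The cost is text only: the sample-size paragraph, with short statements on reporting and on the interim look. The unconditional 80% becomes a conditional range, which is less favourable unless the catheter mean is about 53–60 mg with these SDs.

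### Section 10 withdraws patients with a poor ultrasound view, probably after randomisation, and nothing in the plan keeps them in the primary analysis

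*Combined protocol and SAP*

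**What the plan says.** Section 10 (Withdrawal of Subjects) contains a removal rule: if there was "difficulty with visualization of the TAP plane with ultrasound due to body habitus, then the patient will be withdrawn from the study". The sentence gives no threshold for difficulty, no time relative to randomisation, and no statement on follow-up. It stands in the paragraph about the single injection, ahead of the separate catheter paragraph, and names neither arm.

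The same section words voluntary withdrawal differently by arm. On one side, "patients receiving a single injection are able to withdraw voluntarily any time prior to the injection"; on the other, "With the TAP catheter group, patients may withdraw voluntarily from the study if they wish".

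Section 7 (Procedures Involved) gives the order of events: "Randomization will be performed based on a random number generator (1 or 2) and after patient is consented", and then "the TAP block for both arms will be performed in the preoperative holding area, prior to induction of general anesthesia". In the catheter arm there is an added step: "We will also place peripheral nerve catheters, approximately 3-5cm into the TAP space after injection of the ropivacaine solution". Section 17 adds that "All anesthesiologists performing the TAP block will have had prior education about the proper administration and dilution of the Exparel single shot injections". No blinding is described.

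The statistical section sets 44 per group and continues: "We will enroll 100 to allow for early withdrawal or protocol violations". It names a t-test, a Mann-Whitney U test and a chi-square test. It does not name an analysis population or say what is done with the data of withdrawn patients.

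**The concern.** Randomisation makes the two groups comparable only if those randomised are those compared. A rule that takes patients out of the study after allocation, on a judgement with no stated threshold, by an operator who probably knows the arm, puts that at risk. Body habitus is a baseline trait, so the trait itself is not affected by treatment. The decision that the view is too poor could still differ by arm, because the two procedures differ after the injection and because it is unclear whether the sentence covers both arms.

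If patients leave unequally, and those who leave differ in opioid use, the 48-hour difference no longer compares the randomised groups. Greater loss of high-opioid catheter patients would hide an Exparel benefit. Greater loss of high-opioid Exparel patients would exaggerate one.

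**Working it through.** **Order of events.** Consent, randomisation and the block all take place in the preoperative holding area, in that order (Sections 5 and 7). The eligibility list in Section 4 has no ultrasound scan and no body-habitus criterion. The view is therefore most naturally judged when the block is attempted, after allocation. This is an inference; no section states it.

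**Are withdrawn patients analysed?** The plan enrols 100 against 2 x 44 = 88, a surplus of 12 (12%), to cover withdrawals and violations. It also counts the interim look on patients who complete the study. Both suggest that withdrawn patients are made up from the surplus, not analysed. Again, this is not stated.

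**Reproducing the plan's sample size.**
- Inputs from the statistical section: SDs 17.6 and 19.8 mg, control mean 55.3 mg, a 20% difference, power 0.8, p < 0.05.
- Assumptions: a two-sided test, and 20% taken from the control mean.
- Target: 0.20 x 55.3 = 11.06 mg.
- Pooled SD: sqrt((17.6² + 19.8²)/2) = 18.73 mg.
- n per group = 2 x (1.960 + 0.842)² x 18.73² / 11.06² = 45.03, close to the stated 44.
- Power by the t-test is 0.78 at 44 per group and 0.83 at 50 per group.

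**Illustration of unequal loss.** The loss rates and the opioid excess below are assumptions; the documents give neither. Start from 50 per arm, and let leavers average k x 19.8 mg more opioid than those who stay. Dropping a fraction p lowers an arm's mean by p x k x 19.8, so the shift in the difference is (p₁ - p₂) x k x 19.8.

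| Loss, one arm v the other | n analysed | k | Shift, mg (% of 11.06) | Power, no shift | Power, more loss in catheter arm | Power, more loss in Exparel arm | False-positive rate |
|---|---|---|---|---|---|---|---|
| 12% v 12%, same kind of patient | 44 v 44 | any | 0 | 0.78 | – | – | 0.05 |
| 12% v 4% | 44 v 48 | 0.5 | 0.08 x 0.5 x 19.8 = 0.79 (7%) | 0.80 | 0.74 | 0.85 | 0.055 |
| 12% v 4% | 44 v 48 | 1 | 0.08 x 1 x 19.8 = 1.58 (14%) | 0.80 | 0.67 | 0.89 | 0.069 |

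Power is for a true Exparel benefit of 11.06 mg, evaluated at 11.06 minus the shift (catheter-arm excess) or 11.06 plus the shift (Exparel-arm excess). The higher power in the second case is not a gain, because it comes from an exaggerated difference.

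**Price of keeping these patients.** If retained patients show no treatment difference (an assumption), the effect becomes 11.06 x (1 - p) with 50 per group. Equal exclusion leaves the full effect with 50 x (1 - p) per group. At matched rates:

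| Rate p | Exclude equally: n per group, power | Retain: effect, power |
|---|---|---|
| 4% | 48, 0.82 | 10.62 mg, 0.80 |
| 8% | 46, 0.80 | 10.18 mg, 0.77 |
| 12% | 44, 0.78 | 9.73 mg, 0.73 |

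**The case against.** The strongest reply is that unequal use of the ultrasound rule is not shown. The same service, in the same area, injects the same volume on each side in both arms, and the catheter goes in only after the injection. The view can be judged at a shared step, before treatment, from a baseline trait, and equal use costs only sample size. That stands: knowledge of the arm makes unequal use possible, not certain. What remains is that nothing in the plan ensures equality, and the position of the sentence leaves its scope open.

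A second reply is that the scan may come before randomisation. The documents do not exclude this. If it is so, the protocol should say so.

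A third is that retention costs power at every matched rate. That is correct, and the loss at 12% (0.78 to 0.73) is not trivial.

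A reader might also infer from the voluntary-withdrawal wording that catheter patients will drop out within the outcome window and Exparel patients will not. The text does not support this. It is silent on withdrawal after the injection, part of the contrast is natural because an injection cannot be undone, and nothing says that withdrawal ends collection from the hospital record.

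**Conclusion.** The concern holds in a limited form and should be fixed. The plan contains an explicit removal rule that most likely acts after randomisation, at the discretion of an operator not described as blinded, and no statement keeps the removed patients in the primary analysis. The absence of a named analysis population would alone be a missing detail; combined with this rule it leaves an opening for bias.

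A reader might go further and conclude that the comparison will be biased, or biased for or against Exparel in particular. The documents do not show that. They give no withdrawal rates, no link between imaging difficulty and opioid use, and no time for the judgement. The direction depends on which arm loses more patients. The figures for 12% v 4% illustrate a moderate imbalance and are neither an estimate nor a limit; the 12 surplus patients are a budget, not a cap. I am confident about the rule and the omission, less so about its timing, and I make no claim about the actual size.

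**What to change.** 1. In the statistical section, state that the primary analysis includes every randomised patient in the assigned arm, using the 48-hour opioid total already collected from the hospital stay (Section 7), except where a patient withdraws consent for use of the data.
2. In Section 10, separate not receiving the study block from leaving the study, and state that the rule covers both arms. Clinical handling of these patients stays with the investigators. Alternatively, judge the ultrasound view before randomising, which avoids both exclusion and dilution for this reason.
3. Report withdrawals after randomisation by arm and reason, and present any per-protocol analysis as a sensitivity analysis only.

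The cost is mainly wording, since the outcome is already taken from the record. There are two qualifications. Retention gives somewhat lower power than equal exclusion at the same rate, as shown in the second table. The consent wording, which is not among the documents seen, may need checking to confirm that it allows continued record collection.
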